5.3 REPLACEMENT OF PATIENTS

Randomized patients will not be replaced.

5.4 PRE-TREATMENT ASSESSMENTS

During the pre-treatment period, following signature of the ICF, the Investigator will confirm the patient's eligibility for the study by conducting the assessments summarized in [Table 5](#).

Table 5. Screening period: pre-treatment assessments.

	ASSESSMENT	TIME
1. Written informed consent (general and pharmacogenetic and PGx sub-study)		Before any study procedures.
2. Medical and cancer history/ clinical examination	♦ Demographic data.	Within 28 days prior to first infusion.
	♦ Medical and cancer history/baseline condition: 
 ◦ Primary diagnosis. ◦ Prior treatments (with best response and TTP, when available). ◦ Documented date of relapse. ♦ Disease-related signs and symptoms. ♦ Complete physical examination, including weight, height and calculation of BSA. ♦ Concomitant therapies. 	Within 14 days prior to first infusion.*/**
	♦ Performance status (ECOG PS).	Within 7 days prior to first infusion.*
	♦ Vital signs: heart rate, blood pressure and body temperature.	
3. Laboratory tests	♦ Hematology: differential WBC counts (including neutrophil, lymphocyte and monocyte counts), platelet count and hemoglobin. ♦ Biochemistry: Liver function test (ALT, AST, AP, GGT, total bilirubin; direct bilirubin only if total bilirubin is abnormally high); total proteins, albumin, creatinine, CPK, glucose, calculated CrCL (as per Cockcroft and Gault's formula), and serum electrolytes (Na ⁺ , K ⁺ , Cl ⁻).	Within 7 days prior to first infusion.***
4. Pregnancy test (if women of childbearing potential)	Assessment of β-hCG (urine or serum).	Within 7 days prior to first infusion, if applicable.***
5. ECG	Cardiac rhythm will be identified in ECG intervals of at least 30 seconds of duration, PR interval, QT interval (raw), heart rate and QRS complex.	Within 7 days prior to first infusion.***
6. LVEF	ECHO or MUGA.	Within 14 days prior to first infusion.****
7. PGx	Available stored paraffin-embedded tumor tissue samples; only in those patients that give their written informed consent for the PGx sub-study.	-

	ASSESSMENT	TIME
8. Radiological tumor assessment	Contrast enhanced helical CT-scan or MRI, as clinically relevant.	Within 14 days prior to first infusion.***
9. Tumor marker evaluation	CA-125.	Within 7 days prior to first infusion.***
10. Patient-reported outcomes	EORTC QLQ-C30 and EORTC QLQ-OV28 questionnaires.	Within 7 days prior to first infusion.*
11. Adverse events	Only information on SAEs that occurred after signature of the informed consent is required before treatment start. Grading should be as per the NCI-CTCAE v.4.	-

Regardless of the treatment administered, the same schedule of assessments will apply.

*A 1-day window is allowed for assessment of disease-related signs and symptoms, complete physical examination, ECOG PS, vital signs, and patient-reported outcomes at screening.

**A +1-week window is allowed for medical and cancer history/baseline conditions at screening.

***A +3-day window is allowed for laboratory tests, CA-125 assessment, pregnancy tests and ECG at screening.

****A +2-week window is allowed for LVEF and tumor assessments as per RECIST v.1.1.

ALT, alanine aminotransferase; AP, alkaline phosphatase; AST, aspartate aminotransferase; β -hCG, beta subunit of human chorionic gonadotropin; BSA, body surface area; CPK, creatine phosphokinase; CrCL, creatinine clearance; CT, computed tomography; ECG, electrocardiogram; ECHO, echocardiography; ECOG, Eastern Cooperative Oncology Group; EORTC, European Organization for Research and Treatment of Cancer; GGT, gamma glutamyltransferase; LVEF, left ventricular ejection fraction; MRI, magnetic resonance imaging; MUGA, multiple-gated acquisition scan; NCI-CTCAE, National Cancer Institute Common Terminology Criteria for Adverse Events; PGx, pharmacogenomics; PS, performance status; RECIST, Response Evaluation Criteria In Solid Tumors, SAE, serious adverse event; TTP, time to progression; WBC, white blood cells.

Screening procedures will have to be repeated in case that the first infusion of the study treatment is given out of the established windows.

5.5 PATIENT REGISTRATION

After the patient has signed the ICF, the patient will be registered into the trial and a patient number will be provided. This patient number should be used in all future documentation and correspondence referring to this patient.

5.6 PATIENT RANDOMIZATION

Central randomization will be implemented in all patients that fulfill the inclusion criteria. Randomization of patients should occur as close in time as possible to the administration of the first dose of study drug. Patients will be assigned to each treatment arm at a 1:1 ratio. If the patient had not previously received PLD or topotecan, the assigned treatment in case that the patient is randomized to the control arm (Arm B) will be based on the reported Investigator's preference with regard to each one of these two drugs. However, if the number of patients randomized to either PLD or topotecan reaches 60% of the total number of patients expected in the control arm (i.e. 126 patients), then the treatment of choice in the control arm will be restricted to the less frequent control drug until the end of accrual. Stratification will be performed according to ECOG PS (0 vs. ≥ 1), prior PFI (1-3 months vs. >3 months) and prior chemotherapy (1-2 vs. 3 lines).

5.7 EVALUATIONS DURING TREATMENT

The following assessments will be done while the patient is on treatment ([Table 6](#)).

Table 6. Evaluations during treatment.

	ASSESSMENT	TIME
1. Clinical examination	♦ Complete physical examination, including weight and calculation of BSA.	Cycle 2 and beyond: Day 1 of each cycle (always prior to treatment infusion).*
	♦ Performance status (ECOG PS). ♦ Vital signs: heart rate, blood pressure and body temperature.	Day 1 of each cycle (always prior to treatment infusion).*
	♦ Concomitant therapies.	Throughout the “on treatment” period.**
2. Laboratory tests	♦ Hematology: differential WBC counts (including neutrophil, lymphocyte and monocyte counts), platelet count and hemoglobin. ♦ Biochemistry: Liver function test (ALT, AST, AP, GGT, total bilirubin; direct bilirubin only if total bilirubin is abnormally high); total proteins, albumin, creatinine, CPK, glucose, calculated CrCL (as per Cockcroft and Gault’s formula), and serum electrolytes (Na^+ , K^+ , Cl^-).	Cycle 1: Day 8.* Cycle 2: Day 1 (always prior to treatment infusion) and Day 8.* Cycle 3 and beyond: Day 1 of each cycle (always prior to treatment infusion). * Any patient presenting grade 4 treatment-related AEs should have any relevant tests re-assessed at least within 72 hours until recovery to at least grade 3.
3. Pregnancy test (if women of childbearing potential)	Assessment of β -hCG (urine or serum).	Repeat if applicable.
4. ECG	Cardiac rhythm will be identified in ECG intervals of at least 30 seconds of duration, PR interval, QT interval (raw), heart rate and QRS complex.	Repeat if clinically indicated.
5. LVEF	ECHO or MUGA.	Repeat if clinically indicated. In patients treated with PLD (Arm B), to be repeated every four cycles (or more frequently, if clinically indicated). After exceeding a cumulative anthracycline dose of 450 mg/m^2 , LVEF will be assessed before each PLD infusion.
6. Pharmacokinetics (in the PM01183 treatment arm only)	-	A total of eight blood samples (before PM01183 treatment start, 5 min before the end of PM01183 infusion, and 1 hour and 168 hours after the end of PM01183 infusion) will be collected for pharmacokinetic PM01183 analyses in Cycle 1 (four samples) and in a second cycle (between Cycle 2 and 4) (four samples) in patients treated in Arm A. The second cycle with blood sample collection for PK will be assigned once the patient is randomized into Arm A (see details in Section 7.7.1).
7. Pharmacogenetics	Only in those patients that give their written informed consent for the pharmacogenetic sub-study	One blood sample will be collected before treatment start in patients treated in Arm A along with the first pharmacokinetic sample of Cycle 1 for the pharmacogenetic sub-study.
8. Radiological tumor assessment	Contrast enhanced helical CT-scan or MRI, as clinically relevant.	Every eight weeks from randomization until evidence of PD.*

	ASSESSMENT	TIME
9. Tumor marker evaluation	CA-125.	Every eight weeks from randomization until evidence of PD, but only if baseline levels were higher than normal.*
10. Patient-reported outcomes	EORTC QLQ-C30 and EORTC QLQ-OV28 questionnaires.	Every eight weeks from randomization.*
11. Adverse events	As per NCI-CTCAE v.4.	Throughout the “on treatment” period.**

Regardless of the treatment administered, the same schedule of assessments will apply.

* A 3-day window will be allowed for laboratory tests and ECG, a 1-week window for tumor assessments as per RECIST v.1.1, tumor marker evaluation and patient-reported outcomes, and a 1-day window for clinical assessments (ECOG PS, vital signs, weight, BSA, etc.).

** “On treatment period” = from first infusion of the study treatment (PM01183, PLD or topotecan) to EOT [30 days after the day of the last dose administration, unless the patient starts a new antitumor therapy or dies (whichever occurs first), in which case the date of administration of this new therapy or the date of death will be considered the date of end of treatment].

AE, adverse event; ALT, alanine aminotransferase; AP, alkaline phosphatase; AST, aspartate aminotransferase; β -hCG, beta subunit of human chorionic gonadotropin; BSA, body surface area; CPK, creatine phosphokinase; CrCL, creatinine clearance; CT, computed tomography; ECG, electrocardiogram; ECHO, echocardiography; ECOG, Eastern Cooperative Oncology Group; EOT, end of treatment; EORTC, European Organization for Research and Treatment of Cancer; GGT, gamma glutamyltransferase; LVEF, left ventricular ejection fraction; MRI, magnetic resonance imaging; MUGA, multiple-gated acquisition scan; NCI-CTCAE, National Cancer Institute Common Terminology Criteria for Adverse Events; PLD, pegylated liposomal doxorubicin; PS, performance status; RECIST, Response Evaluation Criteria in Solid Tumors, WBC, white blood cells.

5.8 EVALUATIONS AT END OF TREATMENT

The *end-of-treatment visit* will be scheduled within 30 days (\pm 7 days) after the last treatment infusion, unless the patient starts any subsequent antitumor therapy, in which case the end-of-treatment visit should be performed immediately before the start of the new therapy (ideally the day before or the same day).

Patients, regardless of the reason for ending the treatment, will have to undergo at the end of treatment the following assessments:

- ECOG PS.
- Concomitant therapies.
- Laboratory tests (hematology and biochemistry).
- Pregnancy test (if applicable).
- ECG (if clinically indicated).
- LVEF by ECHO or MUGA (if clinically indicated).
- Radiological tumor assessment (only in those patients who discontinue treatment without radiological PD when the end-of-treatment visit coincides with the planned every-eight-weeks evaluation schedule).
- Tumor marker (CA-125) evaluation, if baseline levels were higher than normal.
- Patient-reported outcomes (EORTC QLQ-C30 and EORTC QLQ-OV28 questionnaires).
- Adverse events.

All these evaluations will only have to be repeated for those parameters for which no measurement is available within 10 days before the end-of-treatment visit, or for those parameters with values that were out of range in the last assessment (grade \geq 2 according to NCI-CTCAE v.4) and considered as treatment-related whenever the medical condition of the patient may allow these evaluations.

Adverse events must be reported for 30 days after the last study treatment administration. All serious adverse events (SAEs) occurring within 30 days of the last study treatment administration or until the start of a new antitumor therapy, whichever occurs first, will be reported. Beyond this period of time, only those suspected to be treatment-related SAEs will be reported (Section [7.4.2](#)).

The Sponsor will evaluate all safety information that is spontaneously reported by an Investigator beyond the time frame specified in the protocol.

5.9 FOLLOW-UP AFTER END-OF-TREATMENT VISIT

Patients who finish treatment without radiological disease progression will be followed every eight weeks (\pm two weeks) from randomization until disease progression or start of a new antitumor therapy, death or until the date of study termination (clinical cutoff), whichever occurs first. Radiological tumor assessments and a tumor marker (CA-125) evaluation (if baseline levels were higher than normal) will be conducted during each of these follow-up visits. After radiological disease progression is documented or a new antitumor therapy is started, patients will be followed at least every three months (\pm two weeks) until death or date of study termination, whichever occurs first. Once the whole recruitment is completed, the 3-month follow-up for patients who discontinue treatment due to disease progression will be performed according to a calendar time. In this survival follow-up, for the purpose of collecting information, a documented telephone call would be acceptable.

The end-of-study date (clinical cutoff) is defined as 24 months after randomization of the last patient. The date and reason of the study discontinuation will be recorded on the patient's CRF (see Section [5.2.1.1](#)).

All AEs suspected to be related to the study treatment must be followed after the end of treatment until the event or its sequelae resolve or stabilize at a level acceptable to the Investigator.

Additional parameters and/or increased frequency of observations should be performed at the Investigator's discretion and according to the nature of the observed AEs. In case of death, autopsy data should be provided when available.

6. TREATMENT

6.1 DESCRIPTION OF TREATMENT

6.1.1 Drug Formulation and Supply

6.1.1.1 Experimental Arm (PM01183): Arm A

PM01183 drug product (DP) presented as a lyophilized powder for concentrate for solution for infusion in 4-mg vials will be supplied by the Sponsor for the purposes of this study.

Before use, the 4-mg vials should be reconstituted with 8 ml of water for injection to give a solution containing 0.5 mg/ml of PM01183. For administration to patients as an i.v. infusion, reconstituted vials are diluted with glucose 50 mg/ml (5%) solution for infusion or sodium chloride 9 mg/ml (0.9%) solution for infusion.

For details on reconstitution/dilution, please refer to the IB and Preparation Guide for Infusion. PM01183 reconstitution/dilution records will be kept by the site.

The full composition of the PM01183 4-mg vials and the reconstituted solution per ml is as shown in [Table 7](#).

Table 7. Composition of lurbinectedin (PM01183) vials.

Component	Concentration/vial	Concentration/vial after reconstitution
PM01183	4.0 mg	0.5 mg/ml
Sucrose	800 mg	100 mg/ml
Lactic acid	22.08 mg	2.76 mg/ml
Sodium hydroxide	5.12 mg	0.64 mg/ml

6.1.1.2 Control Arm (PLD and topotecan): Arm B

- **PLD:**

Commercially available i.v. presentations of vials containing PLD will be provided as appropriate.

- **Topotecan:**

Commercially available i.v. presentations of vials containing topotecan will be provided as appropriate.

PLD and topotecan will be prepared in accordance with the applicable Summary of Product Characteristics. Medication preparation records will be kept by the site.

6.2 ADMINISTRATION OF STUDY MEDICATION

6.2.1.1 Experimental Arm (PM01183): Arm A

Intravenously as a 1-hour infusion through peripheral or central lines.

A minimum total volume of 100 ml, diluted in 5% glucose or 0.9% sodium chloride, to be infused over about one hour, must be used for administration through a central venous catheter, or a minimum 250-ml dilution if a peripheral venous catheter is used.

6.2.1.2 Control Arm (PLD and topotecan): Arm B

- **PLD:**

Intravenously at an initial rate of 1 mg/min through peripheral or central lines. If no infusion reactions are observed, the rate of infusion can be increased to complete the administration of the drug over 1 hour.

Total PLD doses > 90 mg and ≤ 90 mg should be diluted in 500 and 250 ml of 5% glucose solution for infusion, respectively.

- **Topotecan:**

Intravenously as a 30-min infusion through peripheral or central lines.

Topotecan will be diluted in a minimum of 50 ml of 0.9% sodium chloride or 5% glucose solution for infusion.

6.3 STARTING DOSES AND SCHEDULE

6.3.1.1 Experimental Arm (PM01183): Arm A

- 3.2 mg/m^2 on Day 1 q3wk (three weeks = one treatment cycle)

Dose will be rounded to the first decimal.

6.3.1.2 *Control Arm (PLD and topotecan): Arm B*

- **PLD starting dose and schedule:**

50 mg/m² on Day 1 q4wk (four weeks = one treatment cycle).

Dose will be rounded to the first decimal.

Patients previously treated with PLD will be assigned to receive topotecan if they are randomized to the control arm.

- **Topotecan starting dose and schedule:**

- 1.50 mg/m² daily on Days 1-5 q3wk (three weeks = one treatment cycle) for patients with calculated CrCL \geq 60 ml/min.
- 1.25 mg/m² daily on Days 1-5 q3wk for patients with calculated CrCL between 40 and 59 ml/min.
- 0.75 mg/m² daily on Days 1-5 q3wk for patients with calculated CrCL between 30 and 39 ml/min.

Dose will be rounded to the first decimal.

Skipped doses of topotecan will not be replaced.

Patients previously treated with topotecan will be assigned to receive PLD if they are randomized to the control arm.

However, if the number of patients randomized to either PLD or topotecan reaches 60% of the total number of patients expected in the control arm (i.e. 126 patients), then the treatment of choice in the control arm will be restricted to the less frequent control drug until the end of accrual (see Section [5.6](#)).

The dose for all three agents (PM01183, PLD or topotecan) will be capped at a body surface area (BSA) of 2.0 m² in those patients who have a greater BSA. BSA will be calculated according to the standard nomogram used at each center.

6.4 PROPHYLACTIC MEDICATION

All patients will receive standard antiemetic prophylaxis before each treatment infusion, as follows:

- Corticosteroids (dexamethasone i.v. at least 8 mg or equivalent, or at institutional standard antiemetic doses).
- Serotonin (5-HT₃) antagonists (ondansetron at least 8 mg i.v. or equivalent).

If necessary, in addition to the above, the duration of treatment with 5-HT₃ antagonists and/or dexamethasone could be extended. Additional antiemetic agents can be administered as appropriate.

Aprepitant and equivalent agents (e.g., fosaprepitant) are forbidden in patients treated with PM01183.

For the purpose of safety evaluations, an optimal prophylaxis is defined as all the aforementioned allowed medications at their respectively maximum dose.

6.5 CRITERIA FOR TREATMENT CONTINUATION

Further treatment cycles (i.e., Cycle 2 or subsequent) will be administered every three weeks (PM01183 or topotecan) or every four weeks (PLD) (with a window of \pm 48

hours in all three treatment arms) if the patient fulfills all the re-treatment criteria defined in [Table 8](#) (PM01183), [Table 9](#) (PLD) or [Table 10](#) (topotecan).

Table 8. Criteria for treatment continuation with PM01183 (Arm A).

Variable	Day 1
ECOG PS	≤ 2
ANC	≥ 1.5 x 10 ⁹ /l
Platelets	≥ 100 x 10 ⁹ /l
Hemoglobin ^a	≥ 8 g/dl
Total bilirubin	≤ 1.5 x ULN or direct bilirubin ≤ ULN if total bilirubin > ULN
Albumin	≥ 2.7 g/dl
AST/ALT	≤ 3.0 x ULN
CPK	≤ 2.5 x ULN
Calculated CrCl (Cockcroft and Gault's formula)	≥ 30 ml/min
Other non-hematological drug-related AEs (except isolated increased GGT and/or AP; grade 2 alopecia, constipation, fatigue, neuropathy, and not optimally treated nausea)	Grade ≤ 1

^a Patients may receive PRBC transfusion and/or EPO treatment if clinically indicated to increase/maintain adequate hemoglobin levels.

AEs, adverse events; ANC, absolute neutrophil count; AP, alkaline phosphatase; AST/ALT, aspartate aminotransferase/alanine aminotransferase; CPK, creatine phosphokinase; CrCL, creatinine clearance; ECOG PS, Eastern Cooperative Oncology Group performance status; EPO, erythropoietin; PRBC, packed red blood cells; ULN, upper limit of normal.

Table 9. Criteria for treatment continuation with PLD (Arm B).

Variable	Day 1
ECOG PS	≤ 2
ANC	≥ 1.5 x 10 ⁹ /l
Platelets	≥ 75 x 10 ⁹ /l
Hemoglobin^a	≥ 8 g/dl
Total bilirubin	≤ 1.5 x ULN or direct bilirubin ≤ ULN if total bilirubin > ULN
Mucositis or hand-foot syndrome	Grade < 2
Calculated CrCl (Cockcroft and Gault's formula)	≥ 30 ml/min
Other non-hematological drug-related AEs (except isolated increased GGT and/or AP; grade 2 alopecia, constipation, fatigue, neuropathy, and not optimally treated nausea)	Grade ≤ 1

Variable	Day 1
----------	-------

^a Patients may receive PRBC transfusion and/or EPO treatment if clinically indicated to increase/maintain adequate hemoglobin levels.

AEs, adverse event(s); ANC, absolute neutrophil count; AP, alkaline phosphatase; CrCl, creatinine clearance; ECOG PS, Eastern Cooperative Oncology Group performance status; EPO, erythropoietin; GGT, gamma-glutamyltransferase; PPE, palmar-plantar erythrodysesthesia; PRBC, packed red blood cells; ULN, upper limit of normal.

Table 10. Criteria for treatment continuation with topotecan (Arm B).

Variable	Day 1
ECOG PS	≤ 2
ANC	$\geq 1.5 \times 10^9/l$
Platelets	$\geq 100 \times 10^9/l$
Hemoglobin ^a	$\geq 8 \text{ g/dl}$
Total bilirubin	$\leq 1.5 \times \text{ULN}$ or direct bilirubin $\leq \text{ULN}$ if total bilirubin $> \text{ULN}$
AST/ALT	$\leq 3.0 \times \text{ULN}$
Calculated CrCl (Cockcroft and Gault's formula)	$\geq 30 \text{ ml/min}$ ^b
Other non-hematological drug-related AEs (except isolated increased GGT and/or AP, grade 2 alopecia, constipation, fatigue, neuropathy, and not optimally treated nausea)	Grade ≤ 1

^a Patients may receive PRBC transfusion and/or EPO treatment if clinically indicated to increase/maintain adequate hemoglobin levels.

^b Patients with CrCL between 40 and 59 ml/min must be re-treated with no more than 1.25 mg/m² of topotecan daily, and patients with CrCL between 30 and 39 ml/min must receive no more than 0.75 mg/m² of topotecan daily.

AEs, adverse events; ANC, absolute neutrophil count; AP, alkaline phosphatase; AST/ALT, aspartate aminotransferase/alanine aminotransferase; CPK, creatine phosphokinase; CrCL, creatinine clearance; ECOG PS, Eastern Cooperative Oncology Group performance status; EPO, erythropoietin; PRBC, packed red blood cells; ULN, upper limit of normal.

If a patient does not meet the requirements for treatment continuation on Day 1 of any cycle after Cycle 1, re-assessments should be performed within one week, and treatment will be withheld until appropriate recovery, for a maximum of two weeks after the treatment due date. If there is no recovery after a 2-week delay, treatment must be discontinued, except if objective clinical benefit is adequately documented by the Investigator, and upon agreement with the Sponsor. Then, treatment may continue after appropriate dose reduction.

6.6 DOSE REDUCTION

Patients who experience any grade ≥ 3 treatment-related non-hematological toxicity (according to the NCI-CTCAE v. 4) and/or grade 3 thrombocytopenia associated with bleeding or persistent at the time of re-treatment or grade 4, or frequent or prolonged treatment-related dose delays (> 1 week) (or skipped infusions if on topotecan) will continue treatment after appropriate dose reduction (see [Table 11](#) for dose reduction in Arm A, PM01183; see [Table 12](#) for dose reduction in Arm B, PLD or topotecan).

Patients experiencing grade 4 neutropenia or any grade febrile neutropenia, or neutropenic infection during the preceding cycle or frequent treatment-related dose delays exclusively due to neutropenia may continue treatment without any dose reduction, but the patient must receive secondary prophylaxis with CSF starting at least 24 hours after the last infusion of the cycle. If despite appropriate CSF secondary prophylaxis, grade 4 neutropenia or febrile neutropenia, neutropenic infection or the dose delay re-occurs, then dose reduction should be implemented.

Exceptions for dose reduction are: grade 3 nausea and/or vomiting not optimally prevented, grade 3 fatigue lasting \leq 2 days, grade 3 diarrhea lasting \leq 1 day or not optimally treated, isolated grade 3 ALT or AST elevations not leading to dose delays and/or non-clinically relevant isolated biochemical abnormalities (e.g., GGT).

Table 11. Levels of dose reduction in Arm A (PM01183).

	Arm A PM01183 dose (q3wk) (mg/m ²) ^a
1 (starting dose)	3.2
-1	2.6
-2	2.0

^a PM01183 dose will be capped at a body surface area (BSA) of 2.0 m² in those patients who have a greater BSA.

q3wk, every three weeks.

Table 12. Levels of dose reduction in Arm B (PLD or topotecan).

	Arm B			
	PLD^e (q4wk) (mg/m ²)	Topotecan^e daily dose (q3wk) (mg/m ²)		
1 (starting dose)	50	1.50 ^a	1.25 ^b	0.75 ^{c, d}
-1	37.5	1.25	1.00	-
-2	28 ^d	1.00	0.75 ^d	-

^a Starting dose for patients treated with topotecan with calculated CrCL \geq 60 ml/min.

^b Starting dose for patients treated with topotecan with calculated CrCL of 40-59 ml/min.

^c Starting dose for patients treated with topotecan with calculated CrCL of 30-39 ml/min.

^d No dose reduction below 28 mg/m² of PLD or 0.75 mg/m²/day of topotecan will be implemented under any circumstances.

^e PLD and topotecan dose will be capped at a body surface area (BSA) of 2.0 m² in those patients who have a greater BSA.

CrCL, creatinine clearance; PLD, pegylated liposomal doxorubicin; q3wk, every three weeks; q4wk, every four weeks.

In case of grade \geq 2 hand-foot syndrome (HFS) or stomatitis secondary to PLD treatment, the PLD treatment administration will be delayed until resolved to grade \leq 1 or discontinued if not resolved within two weeks. In addition, subsequent doses will be reduced if the HFS or stomatitis is \geq grade 3 ([Table 13](#)).

Table 13. PLD dose modification guidelines according to hand-foot syndrome and stomatitis (Arm B).

Toxicity grade	Hand-foot syndrome (HFS)	Stomatitis	Dose adjustment
1	Mild erythema, swelling, or desquamation not interfering with daily activities.	Painless ulcers, erythema, or mild soreness.	Re-treat unless patient has experienced previous grade 3 or 4 HFS/mucositis. If so, delay up to two weeks and decrease dose one level. Return to original dose interval.
2	Erythema, desquamation, or swelling interfering with, but not precluding normal physical activities; small blisters or ulcerations less than 2 cm in diameter.	Painful erythema, edema, or ulcers, but can eat.	Delay dosing up to two weeks or until resolved to grade 0-1. If after two weeks there is no resolution, PLD should be discontinued. If resolved to grade 0-1 within two weeks, and there are no prior grade 3-4 HFS/mucositis, continue treatment at previous dose and return to original dose interval. If patient experienced previous grade 3-4 toxicity, continue treatment with one dose level reduction and return to original dose interval.
3	Blistering, ulceration, or swelling interfering with walking or normal daily activities; cannot wear regular clothing.	Painful erythema, edema, or ulcers, and cannot eat.	Delay dosing up to two weeks or until resolved to grade 0-1. Decrease dose one level and return to original dose interval. If after two weeks there is no resolution, PLD should be discontinued.
4	Diffuse or local process causing infectious complications, or a bed ridden state or hospitalization.	Requires parenteral or enteral support.	Delay dosing up to 2 weeks or until resolved to grade 0-1. Decrease dose one level and return to original dose interval. If after two weeks there is no resolution, PLD should be discontinued.

HFS, hand-foot syndrome; PLD, pegylated liposomal doxorubicin.

Patients treated with PLD who have LVEF decreased to < 45% or with a 20% decrease from the baseline value have to permanently discontinue PLD treatment.

Control and experimental arms:

Patients who experience any treatment-related grade 3 or 4 hypersensitivity and/or extravasations will permanently discontinue irrespectively of arm allocation.

Up to two dose reductions are allowed per patient. Patients who continue to experience treatment-related toxicity and/or frequent dose delays after two dose reductions must be withdrawn from the study. Once the dose has been reduced for an individual patient, it will not be re-escalated under any circumstances irrespectively of arm allocation.

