5.2.1 Discontinuations

5.2.1.1 Treatment Discontinuation

Treatment discontinuation occurs when an enrolled patient ceases to receive the study treatment (PM01183, PLD or topotecan) regardless of the circumstances. By convention, the date of end of treatment is defined as 30 days after the day of the day of last dose of the study treatment (treatment discontinuation), start of a new antitumor therapy or death, whichever occurs first, in which case the date of administration of this new therapy or the date of death will be considered the date of EOT.

The primary reason for any treatment discontinuation will be recorded on the patient's Case Report Form (CRF).

Should a patient decide to prematurely discontinue the study treatment (refuses treatment), all efforts will be made to complete and report the observations as thoroughly as possible. She should be asked if she can still be contacted for further information. The outcome of that discussion should be documented in the medical records.

5.2.1.2 *Reasons for Treatment Discontinuation*

Patients will receive the study treatment(s) while it is considered to be in their best interest. Specifically, treatment will continue until:

- Disease progression.
- Unacceptable toxicity.
- Intercurrent illness of sufficient magnitude to preclude safe continuation of the study.
- Investigator's decision.
- Patient refusal.
- Non-compliance with study requirements.
- A major protocol deviation that may affect the risk/benefit ratio for the participating patient.
- Requirement of > two dose reductions.

Patients who are withdrawn for any reasons must not be re-treated in the context of this study at any time. For follow-up activities, please refer to Section [5.9](#).

5.2.1.3 *Study Discontinuation*

Study discontinuation occurs when an enrolled patient ceases to participate in the study, regardless of the reason (as detailed under "Follow-up" in Section [5.2](#)). The date and reason for study discontinuation will be clearly documented in the medical records of the patient.

5.2.2 *Protocol Deviations*

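### For topotecan patients at 0.75 mg/m²/day, section 6.6 calls for a dose reduction that Table 12 forbids, and no specific rule says what happens then

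*Protocol*

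**What the plan says.** The first paragraph of protocol section 6.6 opens with "Patients who experience any grade ≥ 3 treatment-related non-hematological toxicity". It adds certain thrombocytopenia, frequent or prolonged treatment-related delays and, for topotecan, skipped infusions. Patients meeting any of these "will continue treatment after appropriate dose reduction", with Table 12 as the reference for Arm B. The second paragraph also ends in a reduction if a neutropenic event or delay recurs despite secondary CSF prophylaxis.

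Section 6.3.1.2 sets the topotecan starting dose in the lowest eligible renal band: "0.75 mg/m² daily on Days 1-5 q3wk for patients with calculated CrCL between 30 and 39 ml/min". In Table 12, footnote c identifies the same group ("Starting dose for patients treated with topotecan with calculated CrCL of 30-39 ml/min"), and both lower dose levels in that column hold a dash. Footnote d, attached to this column, reads: "No dose reduction below 28 mg/m² of PLD or 0.75 mg/m²/day of topotecan will be implemented under any circumstances".

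Two rules tie leaving treatment to the number of reductions. Section 6.6 says "Up to two dose reductions are allowed per patient" and requires withdrawal if toxicity or frequent delays go on after two. Section 5.2.1.2 lists "Requirement of > two dose reductions" among the reasons to stop.

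Section 6.5 adds two points. Footnote b of Table 10 limits re-treatment to 0.75 mg/m²/day when clearance is 30-39 ml/min, so patients who started higher can arrive at the floor. Treatment after a delay of more than two weeks is possible only with documented benefit and Sponsor agreement, and again only after a dose reduction. The synopsis repeats all of this.

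**The concern.** A site with a patient at 0.75 mg/m²/day and a qualifying event is told to continue at a reduced dose and, by the table that the instruction cites, that no reduced dose may be given. Staying at 0.75 departs from the first paragraph of section 6.6; going lower departs from footnote d. Section 5.2.2 gives incorrect dosing through not following dose-adjustment specifications as an example of a deviation that might affect patient safety, and says that deviations affecting risk/benefit will not be authorized. A site could therefore be in deviation whichever way it keeps the patient on treatment.

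These patients have the lowest renal function that the eligibility criteria allow. The protocol (section 1.2.3) names myelosuppression as topotecan's dose-limiting toxicity. If sites resolve the gap differently, management after severe toxicity will vary by site in the control arm.

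**Working it through.** No formula tests the contradiction itself. The check traces each Arm B column of Table 12 against the reduction rule, the floor in footnote d and the withdrawal rules.

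| Table 12 column | Levels (mg/m²) | Reductions available | Can two reductions be reached? |
|---|---|---|---|
| PLD | 50 → 37.5 → 28 | 2 | Yes |
| Topotecan, CrCL ≥ 60 ml/min | 1.50 → 1.25 → 1.00 | 2 | Yes |
| Topotecan, CrCL 40-59 ml/min | 1.25 → 1.00 → 0.75 | 2 | Yes |
| Topotecan, CrCL 30-39 ml/min | 0.75 | 0 | No |

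The first three columns fit the rest of the text: two steps are allowed, two exist, neither step goes below the floor, and the withdrawal rule takes over afterwards. Only the fourth fails. A reduction is called for, none exists, and neither reduction-linked rule can be triggered from zero reductions.

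Three instructions meet the same obstacle in that column: the first paragraph of section 6.6, the recurrence step of its second paragraph, and the section 6.5 condition for continuing after a two-week delay. The list of exceptions to dose reduction in section 6.6 does not mention the column.

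Patients brought to 0.75 later by footnote b of Table 10 are in the same position, unless they have already had two reductions. The protocol does not say whether that renal cap counts as one of the two.

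Size, for starters only:

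- The control arm is 420 / 2 = 210 patients. The cap on either drug is 0.60 × 210 = 126, the protocol's own figure, so the other drug has at least 210 − 126 = 84. Topotecan patients therefore number 84 to 126.
- The documents give no share with clearance of 30-39 ml/min. Assume 2% to 5%.
- Low end: 0.02 × 84 = 1.7. High end: 0.05 × 126 = 6.3. This is about 2 to 6 patients.
- Against 420 randomized: 2/420 = 0.5% to 6/420 = 1.4%. Only those who go on to have a qualifying event meet the contradiction.

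The number capped at 0.75 later cannot be estimated from the documents.

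**The case against.** The strongest reply is that the floor is deliberate and visible. Table 12 prints dashes and attaches footnote d to exactly this column, the text asks for an appropriate reduction, and two reductions is a maximum rather than a promise. The dash could be taken to mean that treatment ends. That is a possible reading, but the protocol does not state it. Where it wants discontinuation elsewhere it says so: in Table 13 for hand-foot syndrome and stomatitis, in the LVEF rule for PLD, and for grade 3-4 hypersensitivity or extravasation.

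A reader might infer that these patients have no stopping rule at all. The documents do not support that. Section 5.2.1.2 lists unacceptable toxicity and Investigator's decision as reasons that do not depend on the number of reductions. Section 6.5 withholds treatment until recovery and, with the one exception noted, ends it after a two-week delay without recovery. Section 6.6 ends it for grade 3-4 hypersensitivity or extravasation. A first grade 4 neutropenia, febrile neutropenia or neutropenic infection at 0.75 also has a workable rule, namely that treatment may continue unreduced with mandatory CSF. What stands is narrower: for the remaining qualifying events, and for recurrence despite CSF, no specific instruction says what to do when the required reduction is unavailable.

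A reader might also infer that grade 3-4 neutropenic infection falls under two opposite rules, the first paragraph of section 6.6 requiring a reduction and the second not. This is not established. The second paragraph names the event and gives it a full sequence: "or neutropenic infection during the preceding cycle or frequent treatment-related dose delays exclusively due to neutropenia may continue treatment without any dose reduction", with CSF, then a reduction on recurrence. Its wording on dose is permissive, so a site that reduces and gives CSF breaches neither paragraph. A conflict needs the event to count as non-hematological, which no section states. The neutropenia and febrile neutropenia rates that the protocol reports are not rates of this event.

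**Conclusion.** The inconsistency holds for topotecan patients at 0.75 mg/m²/day, whether they start there or are capped there later without two earlier reductions. Section 6.6 calls for a reduction, Table 12 and footnote d rule it out, and the reduction-linked withdrawal rules cannot apply. General reasons for stopping exist but leave the outcome to each site.

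This rests on the text alone and needs no assumption. The size does: 2 to 6 starters depends on the assumed 2-5% and on a control arm of 210 split within the 60% cap. With so few patients, no material effect on control-arm exposure or on the primary PFS comparison is shown. The reason to act is that a dosing instruction for a vulnerable group cannot be followed as written, and correcting it is cheap.

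**What to change.** The sponsor's clinical team should reconcile section 6.6, including Table 12 and footnote d, with section 5.2.1.2, section 6.5 (Table 10 footnote b and the two-week-delay text) and the matching synopsis rows on treatment continuation, dose reduction and study duration. The result should be one executable instruction for the case where a reduction is called for and no lower level exists. It should also say whether a renal cap under Table 10 footnote b counts as one of the two permitted reductions. Which instruction is right is a clinical decision, and none is proposed here.

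Optionally, one sentence could confirm that the second paragraph of section 6.6 is the specific rule for neutropenic infection.

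The cost is clarification or amendment text in these sections and the synopsis. No extra patients, data or analyses are needed.
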